#### Measures assessing level of mobility enabled by the exoskeleton to include the following, all measured while subject is using the exoskeleton:

- The 10MWT as a measure of gait speed.
- The TUG test measures ability to independently sit, stand, walk, turn, and return to sitting. The TUG test will be used as a measure of mobility independence.

- The 6MWT measures gait speed over a six-minute period. This test provides a controlled measure of endurance, and provides a secondary measure of gait speed.
- The BRPE measures perceived exertion during walking and will be assessed in this protocol during the 6MWT.

Additional measures taken during each session will include:

- Vital signs at start of each session (blood pressure and heart rate)
- Number of steps taken during each training session (measured by exoskeleton)
- Monitoring of skin integrity at exoskeleton contact points, following each session

Schedule of Assessments

The study will include 4 primary assessments characterizing health and neurological effects of exoskeleton use, in addition to 2 primary assessments characterizing level of mobility provided by the exoskeleton. The assessments characterizing potential health include DXA, MAS, SCI-SET tests, weight, and a self-report questionnaire. The assessments characterizing potential neurological or functional recovery include the MMT and FR tests, and for poorly-ambulatory subjects, also include the FIM-G, WISCI-II, 10MWT, and TUG tests, all performed without the exoskeleton. This battery of assessments is expected to require 3-4 hours, and will occur 4 times during the study as follows: pre-treatment (at study start, session 1), mid-treatment (after 4 weeks of treatment, session 17), post-treatment (after 8 weeks of treatment, session 30), and 8 weeks post-treatment (session 31). Note that DXA will not be measured at mid-treatment, in order to mitigate associated costs, since an 8-week interval is a short enough period of time relative to characteristic time scales associated with changes in BMD. Note that treatment will not occur on these assessment days, i.e., the exoskeleton will not be used on these days. Finally, the MAS will be administered on these 4 days, and also on 3 additional days, each immediately following exoskeleton use associated with a treatment session, at the start, mid-point, and end of treatment.

In addition to assessment of health, neurological and functional status, additional assessments will be performed to characterize the level of mobility provided by the exoskeleton. These assessments include the FIM-G, WISCI-II, 10MWT, 6MWT, TUG, and BRPE tests, all performed while the subject is wearing the exoskeleton. The battery of mobility assessments will occur within the standard treatment sessions at treatment midpoint (i.e., after 4 weeks of treatment, during sessions 15 and 16) and at treatment end (i.e., after 8 weeks of treatment, during sessions 28 and 29). Note that the TUG test is performed on a separate day from the other assessments, to mitigate the number of tests to complete in a single session. Note also that the 10MWT will be administered once during each quarter of treatment, since the test is informative and easily administered, and thus will not substantially disrupt a session of typical exoskeleton treatment.

The scheduling of assessment for each subject is provided in the chart below.

	Outcome Measure	Baseline	Fitting and Training	Treatment (12 sessions)												Mid-treatment	Treatment (12 sessions)															
				Treatment (12 sessions)														Treatment (12 sessions)														
Health effects	DXA																															
	MAS																															
	SCI-SET																															
	Weight																															
	Bloodwork																															
	Self-report																															
Neurological recovery	Neuro exam																															
	FR																															
Neurological recovery for poorly-ambulatory	FIM-G w/o Exo																															
	WISCI-II w/o Exo																															
	10MWT w/o Exo																															
	TUG w/o Exo																															
Mobility (in exoskeleton)	FIM-G																															
	WISCI-II																															
	10MWT																															
	6MWT																															
	TUG																															
Other	BRPE																															
	Steps																															
	Skin																															
	Vital signs																															
	Total session	1	2	3	4	5	6	7	8	9	10	11	12	13	14	15	16	17	18	19	20	21	22	23	24	25	26	27	28	29	30	31
	Total week	1	2	2	2	3	3	3	4	4	4	5	5	5	6	6	6	7	7	7	8	8	8	9	9	9	10	10	11	11	18	
	Treatment session																															
	Treatment week	1	1	1	2	2	2	3	3	3	4	4	4	4	5	5	5	6	6	6	7	7	7	8	8	8	8	8	8	8		

### Schedule of Treatment and Outcome Measures Associated with Study 1

#### Data Analysis

Table 1 lists the relationships between the outcome measures and each hypothesis. Given that each patient is in a chronic stage of injury (i.e., spontaneous changes in health and neurological status are unlikely or minimal), the investigators assume that any statistically significant change in the outcome measures between pre- and post-treatment will have resulted from treatment. Since all measures are quantitative, including the self-report and SCI-SET, testing the respective hypotheses entails testing the extent to which the pre- and post-treatment means, of respective measurements across all subjects, are different. As such, the investigators will employ paired-sample t-tests to test the extent to which pre- and post-treatment means are statistically different, by employing a 95% confidence level in the analysis, unless results indicate a more appropriate confidence level for a given set of data. In addition to using paired t-tests for validating differences in means, and establishing associated confidence levels in those differences, analysis of variance (ANOVA) methods will be employed when determining statistical significance of differences in means between multiple data sets, with 95% confidence levels. Specifically, ANOVA will be used when assessing differences in means between pre-, mid-, post-, and 8-week follow-up measurements. In addition to analyzing results across all subjects, more meaningful results will be provided by separating the subject population into appropriate groups, such as: motor-complete and motor-incomplete individuals; non-ambulatory and poorly-ambulatory ones; individuals with tetraplegia and those with paraplegia; persons with upper paraplegia and those with lower paraplegia; etc. For example, measures associated with walking while not wearing the exoskeleton will only be recorded for poorly-ambulatory individuals; neurological recovery is not expected for individuals with motor-complete injuries (while perhaps possible, such recovery is not hypothesized here); and individuals with tetraplegia are less likely to achieve walking speeds and levels of independence commensurate with community ambulation, relative to individuals with paraplegia. For these groups, ANOVA techniques will be employed to assess differences in

means between groups, in order to indicate and validate differences in outcomes. Software packages facilitating statistical analysis will be employed, including IBM SPSS 22 and MATLAB 2014. Note that a clinical statistician is among the key study personnel associated with this proposal, as outlined in the attached organizational chart.

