### Intervention

The intervention will be carried out identically at all sites and will be comprised of 31 sessions at the subjects' trial site, including 4 assessment sessions (pre, mid, immediately post treatment, and 8 weeks post-treatment), 3 exoskeleton fitting/training sessions, and 24 intervention sessions. The interventions at each site will be administered by a PT experienced in locomotor training for individuals with SCI. Parker Hannifin will provide exoskeleton-specific training at each site, in order to ensure safe, effective implementation and use of the exoskeletons. A summary of each session's activity and measurements follows:

- Session 1: Informed consent and pre-treatment health and neurological assessment, including PT evaluation and Dexa Scan (x-ray picture of the bone) of the distal femur and proximal tibia locations, and drawing about 2 teaspoons (9.5 mL) of blood to check A1C (measures the amount of hemoglobin in the blood that has glucose attached to it) and Lipid Panel to measure cholesterol levels (lasting 4 hrs).
- Sessions 2-4: Exoskeleton fitting, adjustment, and training sessions (3 sessions per week lasting 1.5 hours per session)
- Sessions 5-16: Exoskeleton treatment consisting of walking in the exoskeleton during a 1.5-hr session, with breaks as needed, and with sit-to-stand, turning, and stand-to-sit maneuvers as appropriate (3 sessions per week lasting 1.5 hours). Note that sessions 15 and 16 are additionally used for assessment of the mobility provided by the exoskeleton.
- Session 17: Mid-treatment health and neurological assessment (lasting 3-4 hours).
- Sessions 18-29: Exoskeleton treatment consisting of walking in the exoskeleton during a 1.5-hour session, with breaks as needed, and with sit-to-stand, turning, and stand-to-sit maneuvers as appropriate (3 sessions per week lasting 1.5 hours per session). Note that sessions 28 and 29 are also used for assessment of the mobility provided by the exoskeleton.

- Session 30: Post-treatment health and neurological assessment, within 3 days of session 29, including Dexa Scan (x-ray picture of the bone) of the distal femur and proximal tibia locations, and 2 teaspoons (9.5 mL) of blood to check A1C (measures the amount of hemoglobin in the blood that has glucose attached to it) and Lipid Panel to measure cholesterol levels (lasting 3-4 hours).

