#### Measures assessing physiological (i.e., health) effects:

- DXA: Assessment of changes in BMD over treatment course. Scans will be taken at the distal femur and proximal tibia locations.
- Spasticity rating: MAS, used to assess changes in degree of spasticity over course of treatment. Physical Therapy will assign a gross MAS score for the upper and lower extremities immediately after exoskeleton use as well as on the following day, in order to characterize acute and non-acute effects of exoskeleton use on spasticity.
- SCI-SET: 7-day recall self-report questionnaire that takes into account the effects of spasticity on daily life in people with SCI. Subjects will complete SCI-SET at treatment-start, at mid-point, immediately post-treatment, and at an 8-week post-treatment follow-up.
- Weight: Subjects will be weighed pre-treatment, at treatment midpoint, following treatment, and at an 8 week post-treatment follow-up.
- Subject self-report health questionnaire, including questions regarding pain, spasticity, bowel and bladder function, skin, and well-being.

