#### Measures assessing neurological or functional recovery:

- International Standard for Neurological Classification of SCI (ISNCSCI, R2011). Neurological exams will assess status of neurological recovery. Since inclusion criteria restrict inclusion to chronic injury (i.e., at least 6 months post-injury, preferably at least 1-year post-injury), significant changes in neurological testing would presumably be a result of treatment. This exam will include manual muscle testing (MMT) for subjects with incomplete injury.
- For subjects who are poorly-ambulatory: FIM gait score, WISCI-II rating, 10MWT, and TUG test, all while the subject is not wearing the exoskeleton.
- FR test will be performed while subject is sitting to assess potential changes in trunk control and/or strength.
- Borg Reported Perceived Exertion Scale (BRPE)

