Statistical Analysis Plan

Mobility and Therapeutic Benefits resulting from Exoskeleton Use in a Clinical Setting (SC140121 Study 1)

NCT03082898

[name]

H. Fort Flowers Professor of Mechanical Engineering

Professor of Electrical Engineering

Professor of Physical Medicine and Rehabilitation

[name]

[name]

[name]

Statistical Analysis Plan

Normality of data was determined for each measure by a Kolmogorov–Smirnov (KS) test. All measures were determined to be non-normally distributed, and as such are represented by median and IQR rather than mean and standard deviation. Differences in medians in all measures were tested using a Wilcoxon rank-sum test, with confidence levels for each given by corresponding p values.

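### The protocol credits any significant single-arm pre-post change to treatment, lets the paired-test level follow the results and sets no multiplicity rule, while the SAP reports an unpaired test without naming the contrast

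*Protocol*

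**What the plan says.** **Attribution.** The protocol's Data Analysis section argues that chronic injury makes spontaneous change small, and concludes that "the investigators assume that any statistically significant change in the outcome measures between pre- and post-treatment will have resulted from treatment". The list of neurological and functional recovery measures says, more cautiously, that "significant changes in neurological testing would presumably be a result of treatment". Every subject receives the exoskeleton: "The intervention will be carried out identically at all sites". No control arm or repeated-baseline period is described. Entry is allowed from 6 months after injury, with more than 1 year only preferred (section 4.0).

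**Test and level.** For pre-post comparisons, "the investigators will employ paired-sample t-tests to test the extent to which pre- and post-treatment means are statistically different", at a 95% level "unless results indicate a more appropriate confidence level for a given set of data". That exception belongs to the paired t-tests; the ANOVA sentence has a plain 95% level.

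**Outcomes.** Table 1 has ten rows, nine of them pre-post. No single primary outcome is designated: the Study Outline uses the word primary for a list of measurements, and the Schedule of Assessments uses it for visits. Neither document mentions multiplicity. Table 1 includes neurological recovery in complete injury as a hypothesis, while Data Analysis says recovery in motor-complete injury is not hypothesized.

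**SAP.** It is written in the past tense. It finds all measures non-normal and continues: "Differences in medians in all measures were tested using a Wilcoxon rank-sum test, with confidence levels for each given by corresponding p values". It names no contrast and no significance level.

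**The concern.** Chronicity answers one alternative explanation, natural recovery. It leaves others open.

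- Practice: of the health and recovery tests, the protocol says "This battery of assessments is expected to require 3-4 hours, and will occur 4 times during the study".
- Expectation: pain, bowel and bladder function and well-being are self-reported, and for spasticity "Physical Therapy will assign a gross MAS score for the upper and lower extremities immediately after exoskeleton use". Neither document describes blinded assessment.
- Chance: many outcomes are tested, with no limit on the overall error rate.

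A significance test cannot separate a treatment effect from practice or expectation in a single arm, and adjusting p-values does not help with that. Read literally, a level chosen after results are seen has no defined error rate.

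The SAP raises a separate issue. Leaving the t-test because of non-normality is defensible, but the paired rank test is the signed-rank test. The rank-sum test treats its two samples as independent. If it was run on pre and post values from the same subjects, its p-values are wrong for that comparison and real changes may be missed.

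**Working it through.** The documents give no effect size, SD, correlation or power calculation, so there is no plan figure to reproduce. The sample size, 24, is from the protocol's Design section, and all 24 are taken to have both measurements. All shifts and correlations below are assumptions.

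**1. Non-specific change under the protocol's test.** Paired t-test, two-sided 0.05, 23 degrees of freedom, critical value 2.069. Noncentrality = shift × √24.

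| Shift (SD of change) | Noncentrality | Flagged, per measure |
|---|---|---|
| 0.2 | 0.98 | 16% |
| 0.3 | 1.47 | 29% |
| 0.4 | 1.96 | 47% |

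**2. Number of tests.** The nine pre-post rows of Table 1 hold 1+1+1+2+1+1+2+3+7 = 19 entries. Counting each measure once gives 14: weight, DXA, bowel/bladder, MAS, SCI-SET, pain, well-being, neurological exam, FR, MMT, FIM-G, WISCI-II, TUG and 10MWT. BRPE makes 15: Table 1 and the recovery list include it, but the Schedule of Assessments battery omits it. The four-time-point ANOVA and the open-ended subgroup list are left out, so these counts are low.

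**3. At least one false positive under the paired test with no true effect.** Independent: 1 − 0.95^k. Correlated: equicorrelated normal statistics.

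| k | Independent | Correlation 0.5 |
|---|---|---|
| 14 | 51% | 35% |
| 15 | 54% | 36% |
| 19 | 62% | 41% |

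Some measures are taken only in a subset (walking tests in poorly-ambulatory subjects, MMT in incomplete injury). For a valid test these rates do not depend on n.

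**4. The SAP's test, if applied to pre-post pairs.** Simulated normal data, n = 24, nominal 0.05. The last two rows use a fixed raw shift of 0.6 SD of a single measurement. Since the SD of change is √(2(1 − ρ)), that equals 0.51 / 0.60 / 0.77 SD of change.

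| Pre-post correlation ρ | 0.3 | 0.5 | 0.7 |
|---|---|---|---|
| Rank-sum true size per test | 2% | 0.8% | 0.1% |
| Any false positive, 14-19 independent tests | 25-32% | 10-14% | 2% |
| Rank-sum power | 50% | 51% | 52% |
| Signed-rank power | 63% | 79% | 94% |

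The third line is 1 − (1 − size)^k, for example 1 − (1 − 0.0203)^14 = 25%. The simulated figures are good to about one percentage point.

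**The case against.** **The reported analysis may have few chance findings.** A reader might infer that the SAP's results are more likely than not to contain a false positive. The documents do not support that. The 51-62% belongs to the protocol's paired test with independent measures. With correlated measures it falls below half, and several here overlap (MAS with SCI-SET; FIM-G, WISCI-II, TUG and 10MWT). If rank-sum was used on pre-post pairs, the rate is lower still. This limits the size of the point. But the protection is accidental: it depends on each measure's unknown correlation and is paid for in power.

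**The SAP's test may not be misapplied.** A reader might infer that pre-post data were certainly analysed as unpaired. The SAP names no contrast. Rank-sum would suit between-group comparisons, and the name could be a slip for signed-rank. So the conflict with the protocol is conditional. What stands is that the test is reported for all measures and the reader cannot tell what was compared.

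**The level may only be reported, not moved.** Both documents use confidence level loosely, and the clause could mean quoting attained p-values. Nothing shows that the level was changed, and the ANOVA level is fixed. The wording still permits a change.

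**Attribution is a reasoned assumption.** The protocol does give a reason, and practice cannot affect DXA or weight. DXA is also not taken at mid-treatment. The reason still does not cover self-report, therapist-assigned MAS or repeated performance tests.

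**It is too late to change the plan.** The SAP describes completed tests, so pre-specification cannot be restored. The remedy therefore lies mainly in reporting.

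**Conclusion.** The point holds in this form. The causal reading of a significant pre-post change is not supported by a single-arm design: an assumed non-specific shift of 0.2 to 0.4 SD of change would be credited to the exoskeleton 16% to 47% of the time per measure. This does not show that the treatment has no effect, only that the stated rule cannot tell.

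The paired-test level is not firmly fixed, and no multiplicity rule exists. Under the protocol's test, the chance of at least one false positive is about 35% to 62%, depending on how tests are counted and on correlation between 0 and 0.5. The SAP's rank-sum test, if applied to pre-post pairs, errs the other way: size of 2% or less per test, and power of about half where signed-rank would have 63% to 94%. That part is conditional on a contrast the SAP does not state. The contradiction over complete injury is plain in the text. The point should be addressed, and the cure is inexpensive.

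**What to change.** 1. Replace both attribution sentences, at least in reporting, with wording such as: *a significant result shows change over the treatment period; a single-arm design cannot separate it from practice, expectation or natural change.*
2. Delete the clause that lets the level depend on results, and use two-sided 0.05 throughout.
3. State in the SAP which contrasts were tested. Use Wilcoxon signed-rank for pre-post comparisons and keep rank-sum for between-group comparisons.
4. Report all Table 1 results as exploratory, stating the number of tests under one counting rule (including how BRPE and bowel/bladder are counted). Holm-adjusted p-values are optional and should be labelled post hoc.
5. Reconcile the complete-injury row of Table 1 with Data Analysis, for example by labelling it exploratory.

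**Cost.** Rewording, and a re-run of existing data if rank-sum was used on pairs; no new data. Claims become more modest. Moving from rank-sum to unadjusted signed-rank restores power but raises the chance of any false positive to about 35-62%, so the exploratory label and the test count must go with it. Holm is left optional because it is expensive here: for 14 tests, its strictest step cuts signed-rank power for a change of 0.6 SD of change from about 78% to about 39% at n = 24.

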## 6.0 Study Procedures

### Design:

This study will include 24 non-ambulatory or poorly-ambulatory individuals with chronic SCI, i.e., at least 6 months post-injury, 12 with complete and 12 with incomplete SCI, to assess the mobility and therapeutic benefits resulting from exoskeleton use in a clinical setting. Changes in physiological and neurological status will be assessed via measurements taken pre-, mid-, and post- the 8-week intervention, as well as 8 weeks post-treatment. At all study sites, subject enrollment will begin following IRB approval, with 8 subjects enrolled at each of the 3 sites. Following IRB approval and enrollment, the study is expected to occur over an 18-month period. The treatment for each subject will consist of 31 sessions spanning 18 weeks in total, comprising a combination of 4 assessment, 3 training, and 24 treatment sessions. The 24 treatment sessions each consists of approximately 1 hour of walking in the exoskeleton, although 1.5 hours are allotted to account for donning/doffing, measurement of vital signs, skin checks, etc., and will be delivered 3 times per week over an 8-week period.

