- Session 31: Follow-up health and neurological assessment, including Dexa Scan (x-ray picture of the bone) of the distal femur and proximal tibia locations, and 2 teaspoons (9.5 mL) of blood to check your A1C (measures the amount of hemoglobin in the blood that has glucose attached to it) and Lipid Panel to measure cholesterol levels, 8 weeks following session 30 (lasting 3-4 hours).

Women of child bearing potential will have a urine pregnancy test at baseline, and in sessions 17, 30 and 31.

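### No stated test addresses what happens after treatment stops: the 8-week follow-up enters only a four-visit ANOVA, and the SAP names no pair of visits

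*Protocol*

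**What the plan says.** The protocol's Design paragraph (section 6.0) schedules assessments before, midway through and after the 8-week intervention, "as well as 8 weeks post-treatment". The Intervention list places session 31 "8 weeks following session 30" and repeats DXA and the blood tests there. Table 1 lists the follow-up reading under every hypothesis except community mobility.

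The Data Analysis section names two analyses across visits:

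- Pre versus post: "paired-sample t-tests to test the extent to which pre- and post-treatment means are statistically different".
- All four visits: "Specifically, ANOVA will be used when assessing differences in means between pre-, mid-, post-, and 8-week follow-up measurements".

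A further use of ANOVA in that section compares groups of participants, not visits. No follow-up contrast, post-hoc procedure or estimate of retained change is named.

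The SAP is one paragraph. It summarises measures by median and IQR and states: "Differences in medians in all measures were tested using a Wilcoxon rank-sum test". It names no visit or pair of visits, does not mention the follow-up, and does not carry the ANOVA forward.

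**The concern.** An ANOVA across four visits asks whether any of the visit means differ. It takes no account of the visits' order, or of the fact that the first precedes treatment and the last comes 8 weeks after treatment ended. A significant result is compatible with a gain that lasted and with one that disappeared. The SAP does not fill the gap. A rank-sum test compares two samples, so visits would have to be taken two at a time, but the pairs are not stated. The test also treats repeated readings on the same people as independent.

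At stake is what can be formally concluded from session 31. If its comparisons are not named in advance, they can be chosen after the results are seen, in a plan that already sets its level "by employing a 95% confidence level in the analysis, unless results indicate a more appropriate confidence level for a given set of data". The visit also has some value as a check on attribution. The study has no control group, and the Data Analysis section assumes that a significant pre-post change is due to treatment. For outcomes that reverse quickly, continued improvement after stopping would call that assumption into question. The check is partial, because durable gains also persist and the documents do not say which outcomes reverse quickly.

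**Working it through.** **Inputs from the documents.** The sample size is 24: "with 8 subjects enrolled at each of the 3 sites", and 3 × 8 = 24. The confidence level is 95%, taken here as two-sided 0.05. Health and neurological measures have four visits. DXA and the blood tests have three (sessions 1, 30 and 31). No power calculation, effect size, SD or dropout rate is given, so there is no planned power to reproduce.

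**Assumptions (not in the documents).** Equal variances (SD 1) and equal correlation ρ = 0.7 between visits; gain d = 0.46 SD by session 30; a share m of that gain present at midpoint, varied from 0 to 1; complete data. The ANOVA is taken in its favourable repeated-measures form.

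**Step 1: spread of the visit means.** The F test depends on the means only through the noncentrality λ = n·d²·S/(1 − ρ), where S is the sum of squared deviations of the visit pattern from its own mean.

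- Four visits, gain kept (0, m, 1, 1): S = 0.75m² − m + 1.
- Four visits, gain lost (0, m, 1, 0): S = 0.75m² − 0.5m + 0.75.
- Difference, kept minus lost: (1 − 2m)/4. This is zero at m = 0.5, positive below it and negative above it.
- Three visits, kept (0, 1, 1): S = 2 − 4/3 = 0.667. Lost (0, 1, 0): S = 1 − 1/3 = 0.667. These are identical.

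**Step 2: rejection rates.** λ = 24 × 0.46² × S/0.3 = 16.928 × S, referred to F with 3 and 69 degrees of freedom (four visits) or 2 and 46 (three visits).

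| Pattern | S kept / lost | λ kept / lost | Rejection kept / lost |
|---|---|---|---|
| Four visits, m = 0 | 1.00 / 0.75 | 16.93 / 12.70 | 93% / 84% |
| Four visits, m = 0.5 | 0.6875 / 0.6875 | 11.64 / 11.64 | 80% / 80% |
| Four visits, m = 1 | 0.75 / 1.00 | 12.70 / 16.93 | 84% / 93% |
| Three visits | 0.667 / 0.667 | 11.29 / 11.29 | 84% / 84% |

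With d = 0.5 and ρ = 0.5 the rates at m = 0.5 are 64.2% for both patterns. A simulation of 20,000 trials gave 64.5% kept and 64.2% lost.

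**Step 3: the direct contrast.** For session 31 minus session 30, the paired t noncentrality is d·√n/√(2(1 − ρ)) = 0.46 × 4.899/0.7746 = 2.91 for a complete loss, on 23 degrees of freedom.

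- Gain kept: rejects 5% of the time.
- Gain fully lost: rejects 80%.
- Gain half lost: noncentrality 1.45, rejects 29%.
- Gain fully lost with 12 participants (assumed, for measures taken only in poorly-ambulatory participants): noncentrality 2.06, rejects 47%.

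Over d = 0.3 to 0.8 and ρ = 0.5 to 0.7 with 24 participants, power against complete loss runs from 29% to 99.8%.

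**Step 4: precision.** At ρ = 0.7 the 95% interval for a paired difference has half-width of about 2.069 × 0.7746/4.899 = 0.33 SD with 24 participants and 2.201 × 0.7746/3.464 = 0.49 SD with 12.

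**The case against.** Four objections have force.

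- **Durability is not a stated hypothesis.** Section 2.0 does not mention it, and the Data Analysis section tests the hypotheses by comparing pre- and post-treatment means. That paired test does not use session 31 and is unaffected. This stands, and makes the point secondary. Since Table 1 ties the follow-up to nearly every hypothesis, its analysis should still be stated.
- **A p-value is not the whole report.** A reader might infer that a lasting benefit and a full relapse would be reported identically. The documents do not support that: the SAP summarises measures by median and IQR and, if these are given by visit, the two patterns would look different. What is missing is a test or interval for the difference.
- **Post-hoc comparisons are not excluded.** The protocol speaks only of ANOVA methods, and the SAP's two-sample test could be applied to post versus follow-up. Neither document says that this will be done, and the rank-sum test would ignore the pairing.
- **The direct contrast has limits.** A non-significant session 31 versus 30 result does not establish retention: on the assumptions above it misses a half-lost gain about 71% of the time. This stands and shapes the fix.

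It is also tempting to say that the ANOVA costs power when part of the gain is kept. With half the gain kept at session 31 and half present at midpoint, the ANOVA rejects 65% of the time against 80% for session 30 versus session 1. With none or all of the gain present at midpoint, the ANOVA also reaches 80%, so there is no general penalty.

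**Conclusion.** The point holds as a gap in formal inference on a secondary question. No stated test addresses change after treatment stops, and a significant ANOVA F alone cannot indicate whether a gain lasted.

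A reader might go further and conclude that the ANOVA result is the same whether gains last or vanish. That is exact only for three-visit measures and for four-visit measures with half the gain at midpoint, and only under equal variances and correlations. Elsewhere the rejection rates differ by about 9 percentage points at the extremes. Because the direction depends on how early the gain appears, the difference still tells nothing about durability.

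The percentages rest on the assumed gain and correlation; the algebra in step 1 does not depend on their values. Mobility tests performed in the exoskeleton have no follow-up visit and are not affected.

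**What to change.** For each measure collected at session 31, state these within-person contrasts, each with a 95% confidence interval:

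1. Session 30 minus session 1: the main test, as now.
2. Session 31 minus session 30: change after stopping (secondary).
3. Session 31 minus session 1: retained change (secondary).

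Estimate them from a mixed model with visit as a factor and participant as a random effect, so that one missed visit does not remove a participant. For ordinal or clearly non-normal measures, use paired signed-rank tests with Hodges-Lehmann intervals. The SAP reports all measures as non-normal, so the paired rank version may be the usual one. These replace both the four-visit ANOVA and the unpaired rank-sum test. DXA and the blood tests use the same contrasts without a midpoint visit.

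Judge retention from the interval, not from a non-significant difference. The SAP is written in the past tense; if the data have already been analysed, label the follow-up contrasts post hoc.

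The cost is a few sentences and a standard model, with no new data or visits. The downside is two extra secondary estimates per measure, with low precision in the poorly-ambulatory subset.
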